- For each subject identified in Step 1, generate a continuous response score between 0 (non-response) and 1 (response) using SAS PROC MI adjusting for the same covariates as in the primary analysis. Example SAS code is as follows:

```
proc mi data=a out=xxx seed=1234 n impute=50
    minimum=0 maximum=1;
class treatment sex site discharge discont remdesivir dexamethasone
whostrata;
fcs reg(imputedresp / details);
var treatment sex site discharge discont remdesivir dexamethasone
whostrata imputedresp;
run;
```

- Assign the imputed response (1=response, 0=non-response) based on the response score and the current tipping point. Using the example values above:
 - Given a VERU-111 tipping point response rate of 0.1, subjects in the VERU-111 group with a response score ≥ 0.9 would be imputed as responders and non-responders otherwise.
 - Given a placebo tipping point response rate of 0.4, subjects in the placebo group with a response score ≥ 0.6 would be imputed as responders and non-responders otherwise.
- Then same model as in primary analysis will be run for each pair of response rates and p-values reported in the table. From the table the robustness of results can be evaluated.

[REDACTED]	[REDACTED]

Controlled Quality Management Document		
	Sponsor:	Veru Inc.
	Protocol Number:	V3011902
STATISTICAL ANALYSIS PLAN. PHASE 2-3-4		

6.11.3 Secondary Analyses for the Primary Endpoint

The primary endpoint, mortality rate at Day 60, will also be assessed in the subset of mITT patients and Safety Analysis Set (all treated subjects).

Additionally, similar analysis to primary analysis will be performed in subgroups for region, standard of care, WHO Ordinal Scale at baseline and vaccination status.

To obtain risk differences between treatment groups, the same analysis as described above for primary efficacy analysis will be performed except identity link function will be used. Example SAS code is as follows:

```
proc genmod data=a order=internal;
class treatment sex site remdesivir dexamethasone whostrata;
model response=treatment sex site remdesivir dexamethasone whostrata
  / type3 dist=bin link=identity;
lsmeans treatment / e diff exp cl;
run;
```

Additionally, mortality rates will be summarized using Kaplan-Meier (KM) survival curves and equality of treatment groups will be tested using log-rank test. Hazard ratios will be calculated using the Cox proportional hazards model including terms for treatment, gender, study site (or country or region), remdesivir use (No/Yes), dexamethasone use (No/Yes) and WHO Ordinal Scale strata used in randomization. Any subjects for whom survival status is not available at day 60 will be censored at the day of their last observed assessment or last captured event.

Example SAS code for log-rank test is as follows:

```
proc lifetest data=XXX outsurv=surv1
  plots=survival(atrisk=0 to 60 by 1);
time time*cens(1);
strata treatment;
run;
```

Example SAS code for proportional hazards model is as follows:

```
proc phreg data=XXX;
class treatment sex site remdesivir dexamethasone whostrata;
model time*cens(1)=treatment sex site remdesivir dexamethasone
  whostrata;
```

Controlled Quality Management Document		
	Sponsor:	Veru Inc.
	Protocol Number:	V3011902

```
hazardratio treatment;  
assess ph / resample seed=1234;  
run;
```

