- In patients with a WHO disease severity score of  $\geq 5$  at baseline, the proportion of patients that died on study (up to Day 60) in the placebo group was 46% compared to 10% in the VERU-111 treated group. This represents a 78% reduction in death in the

VERU-111 treated group compared to placebo. It is important to note that in the Phase 2 study, the 6 patients in the placebo group and the 1 patient in the VERU-111 treated group that died on study all had a WHO disease severity score of  $\geq 5$  at baseline. Therefore, randomization into the Phase 3 study will be stratified by WHO scale at baseline such that patients who have a WHO disease severity score of 4, 5, and 6 at baseline are approximately equally distributed between the treatment groups. This is a similar population as was used in the Phase 2 study and accounts for patients that move from WHO severity score of 4 to 5 and then from WHO severity score of 5 to 6 to 7 quickly.

The Phase 2 clinical study was hypothesis generating. A 78-82% reduction in mortality, a 55-65% reduction in death or respiratory failure, 3.2-fold higher mean days in ICU and 3.4-fold higher mean days on mechanical ventilation in the Placebo group compared to the VERU-111 treated group are all clinically relevant observations and warrant the continued development of VERU-111 in the treatment of SARS-CoV-2 in patients at high risk for ARDS.

There were no drug related serious adverse events (SAEs) observed in the Phase 2 clinical study of VERU-111 in SARS-CoV-2 infected patients. There were no drug related serious adverse reactions ( $\geq$ Grade 3).

The relative bioavailability (pharmacokinetics) of the VERU-111 powder in capsule (PIC) formulation has been assessed and compared to a to-be-marketed VERU-111 formulated capsule (FC) formulation. Additionally, the effect of high fat meal (food effect) was also assessed for both formulations. The data are presented in Table 1.

**Table 1 The Steady State Pharmacokinetics of VERU-111 Powder in Capsule (PIC) and Formulated Capsule (FC) Under Fasted and Fed Conditions**

	63 mg PIC (fasted)	63 mg PIC (fed)	31.5 mg FC (fasted)	31.5 mg FC (fed)
N	6	6	6	6
Cmax (ng/mL)	148.1 $\pm$ 64.7	97.8 $\pm$ 53.5	182.2 $\pm$ 32.6	169.9 $\pm$ 104.2
Tmax (hr)	2.17 $\pm$ 0.98	7.67 $\pm$ 2.66	1.67 $\pm$ 1.21	4.08 $\pm$ 2.69
AUC 0-24h (ng $\cdot$ hr/mL)	1006.16 $\pm$ 376.29	984.80 $\pm$ 519.62	973.58 $\pm$ 307.87	1011.27 $\pm$ 512.54

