6.11 Efficacy Analyses

All statistical tests will be performed using a two-tailed 5% overall significance level, unless otherwise stated. All comparisons between treatments will be reported with 95% confidence intervals for the difference.

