(no/yes, populated as ‘no’ for subjects who were not discharged from the hospital prior to withdrawing from the study before Day 60), DISCONT is whether subject discontinued treatment early (no/yes), REMDESIVIR is the use of remdesivir at baseline (no/yes), DEXAMETHASONE is the use of dexamethasone at baseline (no/yes) and WHOSTRATA is the WHO Ordinal Scale strata used in randomization. If the imputation model does not converge when both DISCHARGE and DISCONT variables are included then will be checked if either of them alone can be included in the model. If model converges with DISCHARGE or DISCONT alone but the model with both DISCHARGE and DISCONT does not converge, then imputation model will include only DISCHARGE.

The imputed data sets will be analyzed separately for each imputation using the logistic regression model. If all subjects have the mortality status at Day 60 then the imputation part above will not be used and observed data will be analyzed as such. Example SAS code for logistic regression is as follows:

```
proc logistic data=imputed1 order=internal descending;
by _imputation_;
class imputedresponse treatment sex site remdesivir dexamethasone whostrata
  / param=glm;
model imputedresponse = treatment sex site remdesivir dexamethasone whostrata
  / clodds=both firth;
estimate 'Treatment A vs. Treatment B' treatment 1 -1 / cl e exp;
lsmeans treatment / cl exp diff;
ods output modelanova=imputed_modelanova1
  lsmeans=imputed_lsmeans1
  diffs=imputed_diffs1
  parameterestimates=imputed_parmest1;
run;
```

If there are enough deaths to perform analysis without FIRTH option then it might be dropped out. Note that variable _IMPUTATION_ identifies each of the imputations created by PROC MI.

Finally, results from individual imputations are pooled via Rubin’s rules using PROC MIANALYZE. Example SAS code for pooling log(odds) for each treatment group is as follows:

```
proc mianalyze data=imputed_lsmeans1;
by trt01pn;
modeleffects estimate;
stderr stderr;
ods output parameterestimates=combined_odds1;
```

run;

Example SAS code for pooling log(odds ratio) for each treatment group is as follows:

```
proc mianalyze data=imputed_diffs1;
  modeleffects estimate;
  stderr stderr;
  ods output parameterestimates=combined_diffs1;
run;
```

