6.11.5.2 Days in ICU

‘Days in ICU’ will be summarized using descriptive statistics (n, mean, standard deviation, median, minimum and maximum) by treatment group.

‘Days in ICU’ will be the number of days in ICU up to Day 60. In this analysis the worst possible endpoint will be assigned to those subjects who died at any time up to Day 60. For subjects who died the days in ICU will be set to 60. Even for those who were never in the ICU. If

Controlled Quality Management Document			
	Sponsor:	Veru Inc.	
	Protocol Number:	V3011902	
STATISTICAL ANALYSIS PLAN. PHASE 2-3-4			

subject did not report any days in the ICU then their days will be set to zero except for those who died.

Same analysis will be performed in subgroups for region, standard of care and WHO Ordinal Scale at baseline.

A sensitivity analysis will be performed using the actual number of days in ICU. If subject was never in the ICU then days in ICU will be set to 0 even if subject died.

Treatment comparison will be based on analysis of covariance (ANCOVA) model including treatment as a factor, and study site (or country or region), remdesivir use (No/Yes), dexamethasone use (No/Yes) and WHO Ordinal Scale strata used in randomization as covariates. Treatment difference, standard error, 95% confidence interval and p-value will be presented.

Example SAS codes for the analysis are as follows:

```
proc mixed data=XXX order=internal;
  class trt01pn site remdesivir dexamethasone;
  model response=trt01pn site remdesivir dexamethasone whostrata /
    ddfm=kr;
  lsmeans trt01pn / cl diff;
  ods output tests3=tests lsmeans=lsmeans diff=diffs
  run;
```

6.11.5.3 WHO Ordinal Scale for Clinical Improvement change from baseline to Day 15, Day 22, and Day 29

WHO Ordinal Scale for Clinical Improvement will be summarized in frequency table by visit and treatment group.

Additionally, response status for each subject will be defined based on WHO Ordinal Scale for Clinical Improvement. This analysis will compare subjects that have WHO score 0 or 1 (responder) on the visit to subjects who have WHO score ≥ 2 (non-responder) on the visit.

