14.2.1.11	Proportion of Subjects Alive by Region, Country and Site, and Visit ITT Set	IP	14.2.1.1
14.2.1.12	Logistic Regression for Proportion of Subjects Alive by Region and Visit ITT Set	Stat IP	14.2.1.2
14.2.1.13	Proportion of Subjects Alive by Standard of Care and Visit ITT Set	IP	14.2.1.1
14.2.1.14	Logistic Regression for Proportion of Subjects Alive by Standard of Care and Visit ITT Set	Stat IP	14.2.1.2

	
	
	
	

Controlled Quality Management Document		
	Sponsor:	Veru Inc.
	Protocol Number:	V3011902

Table Number	Table Title	Validation Method	Shell Number (if repeat)
14.2.1.15	Proportion of Subjects Alive by WHO Ordinal Scale at BL and Visit ITT Set	IP	14.2.1.1
14.2.1.16	Logistic Regression for Proportion of Subjects Alive by WHO Ordinal Scale at BL and Visit ITT Set	Stat IP	14.2.1.2
14.2.1.17	Proportion of Subjects Alive by Vaccination Status (All Vaccinated (at Least One Shot) vs. All Unvaccinated) and Visit ITT Set	IP	14.2.1.1
14.2.1.18	Proportion of Subjects Alive by Vaccination Status (All Vaccinated with US Acceptable Vaccine vs. the Rest of the Population) and Visit ITT Set	IP	14.2.1.1
14.2.1.19	Proportion of Subjects Alive by Vaccination Status (All Vaccinated with at Least One Shot within 6 Months of the First Dose on V3011902 vs. the Rest of the Population) and Visit ITT Set	IP	14.2.1.1
14.2.2.1	Proportion of Subjects Alive and Free of Respiratory Failure by Visit ITT Set	IP	14.2.1.1
14.2.2.2	Logistic Regression for Proportion of Subjects Alive and Free of Respiratory Failure by Visit ITT Set	Stat IP	14.2.1.2
14.2.3.1	Descriptive Statistics for Days in Intensive Care Unit (ICU) - Death Assigned to Worst Possible Outcome ITT Set	IP	
14.2.3.2	Analysis of Covariance (ANCOVA) for Days in Intensive Care Unit (ICU) - Death Assigned to Worst Possible Outcome ITT Set	Stat IP	

Controlled Quality Management Document		
	Sponsor:	Veru Inc.
	Protocol Number:	V3011902

Table Number	Table Title	Validation Method	Shell Number (if repeat)
14.2.3.3	Descriptive Statistics for Days in Intensive Care Unit (ICU) by Region - Death Assigned to Worst Possible Outcome ITT Set	IP	14.2.3.1
14.2.3.4	Analysis of Covariance (ANCOVA) for Days in Intensive Care Unit (ICU) by Region - Death Assigned to Worst Possible Outcome ITT Set	Stat IP	14.2.3.2
14.2.3.5	Descriptive Statistics for Days in Intensive Care Unit (ICU) by Standard of Care - Death Assigned to Worst Possible Outcome ITT Set	IP	14.2.3.1

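### Subgroup models for mortality and ICU days are refitted level by level with no treatment-by-subgroup test, so they cannot show whether the effect is consistent

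*SAP*

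**What the plan says.** For Day 60 mortality, SAP 6.11.3 plans that "similar analysis to primary analysis will be performed in subgroups for region, standard of care, WHO Ordinal Scale at baseline and vaccination status". The model to be repeated is in SAP 6.11.1: "model imputedresponse = treatment sex site remdesivir dexamethasone whostrata". It has main effects only. Its output is odds ratios, standard errors, 95% confidence intervals and p-values.

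The table list in SAP 11.1 shows how this is carried out. There is a regression by region (14.2.1.12, "Logistic Regression for Proportion of Subjects Alive by Region and Visit ITT Set"), one by standard of care (14.2.1.14) and one by baseline WHO score (14.2.1.16, "Logistic Regression for Proportion of Subjects Alive by WHO Ordinal Scale at BL and Visit"). For vaccination status, Tables 14.2.1.17 to .19 give proportions only, for example "Proportion of Subjects Alive by Vaccination Status (All Vaccinated (at Least One Shot) vs. All Unvaccinated) and Visit ITT Set".

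SAP 6.11.5.2 repeats the pattern for ICU days: "Same analysis will be performed in subgroups for region, standard of care and WHO Ordinal Scale at baseline". SAP 6.11.5.4 carries it to ventilation days.

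SAP 6.11 sets the default threshold: "All statistical tests will be performed using a two-tailed 5% overall significance level, unless otherwise stated". Nothing different is stated for subgroups. The Holm procedure in SAP 6.11.7 covers overall ICU days and ventilation days, not subgroup results. The only interaction named in either document is treatment-by-visit, in the repeated-measures model of Protocol 9.5.1.2.

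**The concern.** A subgroup analysis of the primary endpoint asks whether the treatment effect is similar across levels. A separate p-value in each level answers another question: whether that level alone, with its own small number of deaths, can exclude no effect. One level can be significant and another not although the true effect is the same in both.

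The plan gives no test that addresses the difference between levels and no statement that the level p-values are descriptive. A reader of the report would have nothing better than a row of significant and non-significant results, and could take a non-significant region or WHO stratum as absence of benefit. With a mortality endpoint, that reading could affect who is thought to benefit.

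**Working it through.** **Inputs.** From Protocol 9.1: 140 and 70 subjects, mortality 5% versus 25%, two-sided alpha 0.05. The documents give no subgroup sizes or level-specific death rates. Equal thirds, equal halves and the other splits below are assumptions.

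**1. The plan's own figures.** SE = √(0.05×0.95/140 + 0.25×0.75/70) = 0.0549. The interval is −0.20 ± 1.96×0.0549 = −0.308 to −0.092, as printed. Pooled-variance power: the pooled rate is 24.5/210 = 0.1167, with null SE 0.0470. Then (0.20 − 1.96×0.0470)/0.0549 = 1.96, which gives 97.5%. This satisfies the stated power of more than 92%. The trial as a whole is not the problem.

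**2. Deaths available.** 140×0.05 + 70×0.25 = 7 + 17.5 = 24.5. One third of the trial has about 8.

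**3. Power inside a level (same pooled formula, 2:1).**

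| Level size | 5% vs 25% | 10% vs 25% |
|---|---|---|
| 105 (half) | 82% | 53% |
| 70 (third) | 67% | 39% |
| 21 (tenth) | 30% | 17% |

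**4. Three equal levels, identical true effect, two-sided Fisher test in each.** Simulation gives:
- 5% vs 25%: all three significant in 23% of trials, mixed in 73%.
- 10% vs 25%: all three in 4%, mixed in 65%, at least one level with no observed benefit in 17%.

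Exact binomial sums for levels of 47/24, 47/23 and 46/23 subjects check this:
- 5% vs 25%: powers 0.633, 0.607, 0.607. All: 0.633×0.607×0.607 = 0.23. None: 0.367×0.393×0.393 = 0.06. Mixed: 1 − 0.23 − 0.06 = 0.71. At least one level with no benefit: 4%.
- 10% vs 25%: powers 0.323, 0.317, 0.299. All: 0.03. None: 0.677×0.683×0.701 = 0.32. Mixed: 0.65. At least one level with no benefit: 19%.

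The two sets differ by a point or two, which does not change the conclusion.

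**5. Other splits (0.5-corrected log odds ratio, Wald test).** Two equal halves give mixed verdicts in 29% (5% vs 25%) and 50% (10% vs 25%). Now take region in two levels, standard of care in two and WHO score at 45/45/10, and condition on a significant overall result. At least one of the seven levels is non-significant in 95% of trials (5% vs 25%) and 98% (10% vs 25%). At least one shows no benefit or a reversal in 20% and 26%.

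**6. The alternative.** A test of heterogeneity between two halves calls a uniform effect inconsistent in 2.7% (5% vs 25%) and 4.1% (10% vs 25%) of trials, and in at most 4.5% in any scenario run. Its power is limited. It is about 61% if the effect is 5% vs 25% in one half and nil in the other, and about 25% if the halves are 5% vs 25% and 15% vs 25%.

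**The case against.** The SAP nowhere says that consistency will be read from level p-values. A reader might infer that it does, but the text only lists the analyses. Level odds ratios with confidence intervals are already planned, and SAP 6.11.7 licenses no subgroup claim. All of this stands, and it limits the point to a missing test and a missing label.

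Three stronger readings are tempting, and the documents do not support them.

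- **Redundant covariates spoil the models.** The subgroup is the baseline WHO score, while the covariate is the stratum used at randomization. SAP 6.1.3 foresees that some subjects were randomized on a wrong score, so the two can differ. Site and country vary within a region, and only the region fallback coincides with the factor. The standard-of-care levels are not defined. A covariate that is constant within a level does not move the treatment estimate.
- **Most trials will show a WHO stratum with no benefit.** About 61% can be obtained by assuming shares of 40/45/15% and mortality of 1/2%, 5/30% and 15/60%. Those odds ratios are about 0.49, 0.12 and 0.12, so the effect is not uniform. The figure also counts as no benefit the roughly one third of trials with no WHO 4 deaths in either arm (0.99^56 × 0.98^28 = 0.32). Strict reversal occurs in about 25%. With a uniform odds ratio of 0.158 and assumed placebo risks of 10/28/50%, no benefit in some stratum falls to about 11 to 12%.
- **WHO 4 will have almost no deaths.** Protocol 3.3 says of "the 6 patients in the placebo group and the 1 patient in the VERU-111 treated group that died on study" that all scored 5 or more at baseline. Working back from 46% (6 deaths) and 10% (1 death), about 13 + 10 = 23 of the 39 patients scored 5 or more, which leaves about 16. The exact upper 95% limit for 0/16 is 1 − 0.025^(1/16) = 21%. Sparse data there are possible, not established.

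It is also fair that an interaction test has low power and does not make level estimates more precise. The SAP amendment log records the mortality subgroups as a regulator's request, so removing those tables would be unwise.

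**Conclusion.** The point holds as a gap in the planned subgroup analysis. Separate refits by region, standard of care and baseline WHO score have no treatment-by-subgroup test and no descriptive label. For a uniform effect across three equal levels, mixed significance is the usual result: about 71 to 73% of trials at the design rates and about 65% at 10% versus 25%. Reversed or absent benefit in some level is much less common: about 3 to 4% and 17 to 19% in those two cases, and about 20 to 26% across the assumed seven levels. It should not be described as near certain.

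These sizes rest on assumed subgroup shares, equal risk across levels and unadjusted tests rather than the planned penalized model. For vaccination status the refit is promised in the text but absent from the table list. The primary test, its alpha and its estimand are not affected. This is a worthwhile correction rather than a threat to the main result.

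**What to change.** 1. In SAP 6.11.3, add one model on all ITT subjects for each subgroup factor: the primary covariates, the subgroup factor and treatment-by-subgroup, keeping the Firth penalty. Report a single interaction p-value beside the level odds ratios and 95% confidence intervals.
2. Keep Tables 14.2.1.12, .14 and .16, and label their level p-values as descriptive.
3. Drop any covariate that coincides with the subgroup factor in a given model.
4. Use the same form for ICU days and ventilation days (treatment-by-subgroup in the ANCOVA).
5. Reconcile the vaccination wording in SAP 6.11.3 with Tables 14.2.1.17 to .19: either add the model or say that proportions only are intended.
6. State that the interaction test has low power at N=210, that a non-significant result does not prove consistency, and that estimates in sparse levels (possibly WHO 4) stay imprecise.

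The cost is SAP wording, a few lines of code and one extra column or table per factor. No new data are needed.

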Controlled Quality Management Document		
	Sponsor:	Veru Inc.
	Protocol Number:	V3011902
STATISTICAL ANALYSIS PLAN. PHASE 2-3-4		

Statistical Analysis Plan

Title: Phase 3, Randomized, Placebo-Controlled, Efficacy and Safety Study of
 VERU-111 for the Treatment of Severe Acute Respiratory Syndrome Coronavirus
 2 (SARS-CoV-2) in Patients at High Risk for Acute Respiratory Distress
 Syndrome (ARDS)

Protocol Number: V3011902

Protocol Version: 1.0 (08-MAR-2021), 2.0 (27-APR-2021), 3.0 (12-MAY-2021),
 4.0 (03-AUG-2021), 5.0 (10-SEP-2021), 6.0 (09-JAN-2022), 7.0 (18-MAR-2022)

SAP Version 5.0

SAP Issue Date: 30-JUN-2022

SAP Author: [REDACTED]

Previous SAP Versions

Version 1.0 (11-FEB-2022), Version 2.0 (16-MAR-2022), Version 3.0 (18-MAR-2022), Version 4.0 (07-APR-2022)

Controlled Quality Management Document			
		Sponsor:	Veru Inc.
		Protocol Number:	V3011902
STATISTICAL ANALYSIS PLAN. PHASE 2-3-4			

SAP Amendments before database lock

Version	Issue Date	Section	Revision / Addition	Rationale
1.0	11-FEB-2022			First Version
2.0	16-MAR-2022	1 and 5 6.11.1, 6.11.3, 6.11.5.2 6.11.1 6.14.1 6.14.1, 11.1	Reworded 'screening' to 'baseline' in randomization strata. Allow model to include country as covariate instead of study site. Updated SAS code for imputation model. Added clarifications for study site variable. Added clarifications for DISCHARGE and DISCONT variables. Updated TEAE definition. Added tables for TEAEs leading to treatment modification, TEAEs leading to treatment discontinuation and Fatal TEAEs.	Consistency with the protocol. To allow model modification i.e. if model does not converge. FDA request. FDA request. FDA request.
3.0	18-MAR-2022	1 4	Added new version of the protocol. Updated for new sample size.	Protocol update. Sample size changed from 300 to 210. Protocol update.
4.0	07-APR-2022	6.11.1, 6.11.3, 6.11.5.2	In the statistical models allowing also region as covariate	Some countries h[redacted] only very few subjects so

[redacted]	[redacted]

Controlled Quality Management Document		
		Sponsor: Veru Inc.
		Protocol Number: V3011902
STATISTICAL ANALYSIS PLAN. PHASE 2-3-4		

		6.11.3, 6.11.5.2, 11.1	Added subgroup analyses for primary endpoint	model fitting might have issues. FDA request
5.0	30-JUN-2022	6.2.1	Updated baseline definition to match protocol.	Clarifications during output production.
		6.2.2	Allow study day derivation to use randomization date for those subjects who were not treated.	Clarifications during output production.

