6.11.1 Primary Efficacy Analysis

The primary endpoint for the study will be the proportion of subjects that die on study (up to Day 60). Responders are subjects who are alive at Day 60.

The number and percentage of deaths will be summarized by treatment group.

Mortality rates will be analyzed using a logistic regression model. The model will include treatment as a factor and gender, study site (or country or region), remdesivir use (No/Yes), dexamethasone use (No/Yes) and WHO Ordinal Scale strata used in randomization as covariates. The model will be fitted using logit link function. Odds ratios, standard errors, 95% confidence intervals and p-values for the treatment difference will be presented.

The primary analysis will be performed on the ITT analysis set and the ITT data scope regardless of patient's use of rescue medications, protocol violations or investigational product discontinuation consistent with the treatment policy strategy. Every effort will be made to collect vital status up to the end of the study period. Missing data for subjects who are lost to follow up will be imputed using multiple imputation methods.

Example SAS code for imputation is as follows:

```
proc mi data=xxx out=imputed1 seed=1234 n impute=50;
class treatment sex site discharge discont remdesivir dexamethasone whostrata
imputedresponse;
fcs logistic(imputedresponse / details likelihood=augment);
var treatment sex site discharge discont remdesivir dexamethasone whostrata
imputedresponse;
run;
```

where IMPUTEDRESPONSE is the response variable to be imputed, TREATMENT is the randomized treatment group (veru/placebo), SEX is sex of the subject (male/female), SITE is study site (if there are issues fitting imputation model then this might be replaced with country or region), DISCHARGE is whether the subject was discharged from the hospital at any time during the study

Controlled Quality Management Document	
	Sponsor: Veru Inc.
	Protocol Number: V3011902
STATISTICAL ANALYSIS PLAN. PHASE 2-3-4	

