6.11.5.5 Days in hospital

‘Days in hospital’ will be summarized using descriptive statistics (n, mean, standard deviation, median, minimum and maximum) by treatment group.

‘Days in hospital’ will be defined using two different algorithms similarly to ‘Days in ICU’.

‘Days in hospital’ will be analyzed using the same methodology as for ‘Days in ICU’ and the same sensitivity analysis will be performed except the subgroup analyses will not be performed.

6.11.5.6 The proportion of subjects that die on study at Day 15, Day 22, and Day 29.

The number and percentage for all-cause mortality will be summarized by treatment group and visit.

These endpoints will be analyzed using the same methodology as for the primary endpoint (separate analysis will be performed for each visit):

- Multiple imputation + logistic regression model
- Risk differences between treatment groups (using identity link function).

Controlled Quality Management Document			
	Sponsor:	Veru Inc.	
	Protocol Number:	V3011902	
STATISTICAL ANALYSIS PLAN. PHASE 2-3-4			

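### The adjusted risk difference comes from an unpenalized identity-link binomial model whose fit, at the planned death rates, almost always ends on the boundary; changing to country or region does not cure this, and no alternative estimator is named

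*SAP*

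**What the plan says.** SAP 6.11.3 obtains the risk difference by a cross-reference to the primary model: "the same analysis as described above for primary efficacy analysis will be performed except identity link function will be used". Protocol 9.4.2 plans the same. The example code begins "proc genmod data=a order=internal", and its model line is "model response=treatment sex site remdesivir dexamethasone whostrata", with a binomial distribution and an identity link. It contains no penalty. For mortality at Days 15, 22 and 29, SAP 6.11.5.6 lists "Risk differences between treatment groups (using identity link function" among the analyses, and Table 14.2.1.8 in SAP 11.1 confirms an identity-link analysis by visit.

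The primary logistic model in SAP 6.11.1 differs in two ways. Its code includes the Firth penalty and runs within each imputed dataset. On the penalty the text adds "If there are enough deaths to perform analysis without FIRTH option then it might be dropped out". Its geographic term may be site, country or region, and the cross-reference carries this option into the risk-difference model. Within 6.11.1 a trigger for the change is written only for the imputation model: "if there are issues fitting imputation model then this might be replaced with country or region". The SAP amendment table, which lists 6.11.3 among the sections concerned, gives the reason for allowing country as "To allow model modification i.e. if model does not converge".

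No section names another estimator of the risk difference if the identity-link fit fails or reaches the boundary.

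**The concern.** An identity-link binomial model adds covariate effects directly to the risk, so every fitted risk must stay between 0 and 1. When deaths are few and covariates many, the likelihood often keeps rising until some subgroup has a fitted risk of exactly 0. The maximum then lies on the edge of the permitted range. The score equations are not solved there, and the usual large-sample argument for the estimate and its Wald interval does not apply. The SAP protects the logit model against sparse deaths but leaves this more fragile model unprotected.

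At stake is the adjusted risk difference and its confidence interval. This is the only planned model that gives an interval on the scale on which Protocol 9.1 tabulates the expected precision.

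**Working it through.** **1. The plan's own figure.** Protocol 9.1 gives 140 and 70 subjects with mortality of 5% and 25%.

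- SE = √(0.05×0.95/140 + 0.25×0.75/70) = 0.0549.
- Interval = −0.200 ± 1.96 × 0.0549 = [−0.308, −0.092].

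This matches the protocol. It is an unadjusted interval. A treatment-only identity-link model is harmless here: it reaches the boundary essentially only if no VERU-111 subject dies, with probability 0.95^140 = 0.08%.

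**2. Expected deaths.** 140 × 0.05 + 70 × 0.25 = 7 + 17.5 = 24.5.

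**3. Why a site term fails.** In a site without a death, lowering the site's coefficient raises the likelihood until a fitted risk there is 0. With S equal sites of size m = 210/S, the chance that a given site has no death is q = 0.95^(2m/3) × 0.75^(m/3). The chance of at least one such site is about 1 − (1 − q)^S.

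| Sites (assumed) | m | q | At least one site without a death |
|---|---|---|---|
| 10 | 21 | 0.065 | 49% |
| 15 | 14 | 0.162 | 93% |
| 20 | 10.5 | 0.255 | 99.7% |

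**4. Why removing site is not enough.** Sex, remdesivir, dexamethasone and three WHO strata form 2 × 2 × 2 × 3 = 24 covariate patterns. Only 7 deaths are expected on VERU-111, at a mean risk of 5%. Chance variation in the additive effects is enough to push the lowest-risk pattern to 0.

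**5. Simulation.** Trials of 210 subjects were randomized 2:1 within WHO strata, and the constrained maximum was found by a log-barrier Newton method. A general-purpose constrained optimizer gave the same log-likelihood in 59 of 60 datasets checked. Assumed inputs:

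- WHO 4/5/6 mix of 40/40/20%, 45/45/10% or equal thirds
- male 50–70%, remdesivir 2–50%, dexamethasone 50–98%
- WHO gradient from none to strong
- geographic levels of unequal size

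Most scenarios used 200 to 700 runs. Share of fits on the boundary, as the range over these inputs:

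| Mortality, VERU-111/placebo | Expected deaths | No geographic term | 3 regions | 20 sites |
|---|---|---|---|---|
| 5%/25% | 24.5 | 94–100% | 99–100% | 100% |
| 10%/25% | 31.5 | 59–94% | 88–99% | 100% |
| 15%/25% | 38.5 | 34–95% | 69–99.6% | not tabulated |
| 15%/30% | 42 | 31–84% | 64–98% | 100% |

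For Days 15, 22 and 29, if 40–80% of the deaths have occurred (9.8 to 19.6), the share is 98–100%.

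**6. What the boundary does at 5%/25%.** Under one set of inputs the constrained estimate averaged −0.185 with region (crude −0.200) and −0.176 with 20 sites (crude −0.205). The pull depends on the WHO gradient: with region, a separate set of inputs gave −0.199 with no gradient and −0.180 with a strong one. The two usual standard errors no longer agree:

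| Geographic term | Mean SE, observed information | Mean SE, expected information | Actual SD | 95% CI coverage, observed / expected |
|---|---|---|---|---|
| Region | 0.070 | 0.052 | 0.060 | 95% / 89% |
| 20 sites | 0.092 | 0.050 | 0.069 | 97% / 82% |

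**7. A replacement.** The standardized difference from the Firth logistic model with region, where the data came from 20/40/60 sites:

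- true difference −0.200: mean −0.204/−0.202/−0.206, coverage 94.7/95.6/94.8%
- 10%/20%, true difference −0.100: mean −0.104/−0.102/−0.104, coverage 95.1/93.8/95.3%

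Standardizing from the model with site does worse. Penalizing many site terms adds predicted deaths (31.3 with 20 sites and 35.2 with 40, against 24.7 observed), and the mean difference becomes −0.215/−0.224/−0.236.

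**The case against.** **The SAP has a fallback.** This stands in part. The cross-reference and the amendment table allow site to be replaced by country or region, so a reader who infers that there is no fallback at all goes too far. What is missing is a fallback estimator. The geographic change leaves 99–100% of fits on the boundary with 3 regions.

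**The code is only an example.** This stands. A reader might infer from the code that the risk difference will ignore imputation. The governing sentence calls for the same analysis as the primary one, which can be read as including imputation, so the omission is a drafting point.

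**The harm is modest.** This stands in part. With observed information the intervals covered 95–97%, and the bias is towards no effect. A reader might infer that the reported interval will certainly be too narrow, or will vary with software settings. That is not shown: SAP 6.3 fixes SAS 9.4 or higher, and the simulations did not run the SAS procedure or establish which information matrix it uses. What remains is that Wald theory does not justify either interval on the boundary.

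**The primary analysis is unaffected.** This stands. A reader might infer from the open wording on Firth and on the geographic term that the primary test is compromised. The coded model (site with Firth) rejected in 4.0–4.3% of trials without an effect, at the 0.0452 level, and had 92.7–97.9% power at 5%/25% with 20 to 60 assumed sites. Dropping Firth with region changed the verdict in 0–1.2% of trials. With Firth kept, the choice of geographic term mattered in 1.5–6.8% of trials at 5%/25% and in 16–23% at 10%/20%. Nothing in the documents says that the choice would be made after unblinding.

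**Conclusion.** The concern holds for the risk-difference model in SAP 6.11.3 and 6.11.5.6. At the planned death rates its maximum lies on the boundary in nearly every trial, whichever geographic term is used and even with none. The usual Wald interval then has no sound basis, and the estimate tends towards 0 when there is a geographic term or a WHO gradient.

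The near-certainty belongs to the planning rates. With more deaths the share falls, to about 34–95% with no geographic term at 15%/25%. The numbers of sites and regions, the WHO and covariate mixes and the timing of deaths are assumptions. The result at 24.5 deaths held across all the mixes tried. The size of the bias and of the difference between standard errors depends more on those inputs.

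The consequence is limited. The analysis is supportive and lies outside the primary test and the Holm family of SAP 6.11.7. Crude rates, the log-rank test and the Cox model remain, and an unadjusted interval follows from the reported counts. It should still be corrected, because the plan as written is likely to yield an unreliable adjusted estimate and interval. The wording on Firth and on the geographic term in 6.11.1 needs clarification only.

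**What to change.** In SAP 6.11.3 and 6.11.5.6, replace the identity-link model by the standardized (g-computation) risk difference from the Firth logistic model with treatment, sex, remdesivir, dexamethasone, WHO stratum and region. Do not use site. For each subject, predict the risk of death under each treatment, average over the ITT set and take the difference, with a delta-method standard error. Compute it in each imputed dataset and pool by Rubin's rules. If no vital status is missing, apply it once to the observed data. Define region, and list the change in SAP section 9, since Protocol 9.4.2 specifies the identity link.

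As a minor clarification in 6.11.1, keep Firth unconditionally. State the order site, country, region, with a fitting trigger checked on blinded pooled data.

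The cost is SAP wording and code. The risk difference is no longer a model coefficient, and it may use a different geographic term from the primary model. Firth shifts it slightly away from 0, by about 0.002–0.006 in the runs above.
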